1.2.9 Change in regrowth rate as endpoint

Although vaccines have improved overall survival in mCRPC, they have not been shown to change short term TTP when used as monotherapy. Interestingly, similar findings were also seen with ipilimumab in melanoma (40). Although this is not what is customarily seen with cancer treatments, it may be a characteristic of modern immune therapeutics (41). An emerging mechanism to evaluate tumor growth rates using mathematical models may provide additional insight into this phenomenon(42, 43). In a recent review of 5 NCI mCRPC trials including a vaccine trial, there appeared to be a sustained decrease in tumor growth rate in vaccine patients as compared to those treated with chemotherapy, who had transient reductions in tumor size, but then growth rate resumed at the same pre-treatment rate once cytotoxic therapy was discontinued. (44) This data suggests that a vaccine induced immune response may not decrease tumor size (or change TTP) but may lead to altered tumor growth rates which could have more substantial impact on overall survival (41). (See Figure 9)

[figure not shown]

Figure 8. PSA-TRICOM can affect growth rate in 80 days. An analysis of the ECOG trial 9802, which treated castration-sensitive non-metastatic prostate cancer patients (n=29) suggests PSA-TRICOM alters tumor growth rate, as measured by PSA ($\log g$ (growth rate) +/- SE (standard error)), within 80 to 100 days.(45) This retrospective analysis used the tumor growth rate equation (44) determined that by day 80 after PSA-TRICOM therapy was initiated a statistically significant change in tumor growth rate was detectable compared to baseline. This altered growth rate was sustained at day 100 as well. These data supports the hypothesis that vaccines exert their therapeutic effect not by reducing tumor burden, but by altering tumor growth rate.

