2.4 TREATMENT ASSIGNMENT AND RANDOMIZATION/STRATIFICATION PROCEDURES

Cohorts

Number	Name	Description
1	Cohort 1	Patients with nonmetastatic castration sensitive prostate cancer

Arms

Letter	Name	Description
A	Standard dose enzalutamide alone	Enzalutamide alone administered at the standard dose (160 mg daily)
B	Enzalutamide with PSA-TRICOM	Standard dose enzalutamide with concomitant vaccinia-PSA-TRICOM and then fowlpox-vaccine

Stratifications

Name	Distinct Options	Notes
PSA doubling time less than 6 months	Yes No	

Randomization and Arm Assignment

After confirmation of eligibility at Central Registration Office (CRO), patients in cohort 1 will be randomized on a 1:1 basis between arms A and B, stratifying for PSA doubling time using a computerized randomization process.

CRO staff will send a secured e-mail to Principal Investigator and research nurse with the Verification of Registration of the patient and treatment arm patient is randomized. This process will be completed within 15–30 minutes of faxing the eligibility checklist. CRO will keep track of all randomization data in Clinical Data Registry (CDR) of CRO.

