8 STATISTICAL CONSIDERATIONS

8.1.1 Cohort 1

The primary objective of this study is to compare the change in the growth rate in the two arms from the time of discontinuation of enzalutamide (3 months after enrollment) to 4 months after completing enzalutamide therapy +/- PSA-TRICOM (7 months after enrollment). With growth rate changes obtained on all patients on both arms, and if the growth rate changes in the two arms had the same standard deviation, with 17 patients per arm, there would be 80% power to detect a difference between the arms equal to 1 SD of the difference from baseline to 7 months with a two-tailed 0.05 significance level two-group t-test. Thus, a total of 34 evaluable patients

are required for analysis. To allow for a small number of patients who do not develop a 25% decline in PSA after 3 months, additional patients will be randomized if necessary to obtain a minimum of 17 evaluable patients on each arm. In order to allow for a small number of such patients, the accrual ceiling will be 38.

Patients will be stratified based a doubling time of greater than or less than 6 months.

Secondary endpoints will be compared between the two arms using appropriate non-parametric tests, such as a Wilcoxon rank sum test. Results will be presented without formal adjustment for multiple comparisons but reported in the context of secondary evaluation of a potentially large number of endpoints. The significance of paired hormone level results within arms will be determined by a paired t-test or Wilcoxon signed rank test as appropriate.

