8.1.3 The regression-growth equation

The equation is $f(t) = \exp(-d * t) + \exp(g * t) - 1$ (A) where \exp is the base of the natural logarithm, $e = 2.7182$, and $f(t)$ is the tumor (or in MTC calcitonin) measurement at time t in days, normalized to (divided by) the tumor measurement at day 0, the time at which treatment is commenced. Rate constant d (decay, in days^{-1}) represents the exponential decrease/regression of the a serum tumor marker (i.e. PSA) signal during therapy. Rate constant g (growth, also in days^{-1}) represents the exponential growth/regrowth of the tumor during treatment. These rate constants may be expressed in terms of half-lives and doubling times. Thus, d equals $\ln_2(0.693)$ divided by the time it takes for the regressing part to shrink by half, whereas g equals \ln_2 divided by the time for the growing component to double. (44)

Two earlier papers depict theoretical curves depicting the separate components of Equation (A) and how these combine together to give the time dependence of the tumor size, f . (44) When the data showed a continuous decrease from the time of treatment start, so that only the regression parameter d was found to differ significantly from zero with $P < 0.05$, Equation (A) was replaced by the following reduced form, with the growth rate constant eliminated: $f(t) = \exp(-d * t)$ (B) When tumor measurements showed a continuous increase, so that only the growth parameter g was found to differ significantly from zero with $P < 0.05$, Equation (A) was replaced by the following reduced form, with the decay constant eliminated: $f(t) = \exp(g * t)$.

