8.1.4 Data Analysis

For each patient an attempt to fit Equation (A) to each data set for which more than one data point is available. Curve fitting will be performed using Sigmaplot (Systat Software), or by

Version Date: 12/5/17

Abbreviated Title: Enzalutamide in non-met CSPC

using the Solver routine in an Excel spreadsheet. We will extract parameters g and d with their associated Student's t and P values. (44) Data will be analyzed in Excel (Microsoft) and in Sigmaplot 9.0. Linear regressions to evaluate the relationship between the growth rate constant, g , or other parameters will be implemented using the polynomial linear routine of Sigmaplot 9.0. Sample comparisons were performed by Student's t -test, using SigmaStat 3.5 (Systat Software), with P set at 0.05 for significance. (44)

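### A per-patient P<0.05 test in 8.1.3 can remove the primary-endpoint parameter g, and the plan does not say what growth value such a patient then contributes

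*Combined protocol and SAP*

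**What the plan says.** Section 8.1.3, which repeats 1.2.10.1, fits Equation (A), f(t) = exp(-d·t) + exp(g·t) - 1, with day 0 at the start of treatment. It then gives two reductions.

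- If the series falls continuously and only d has P<0.05, "Equation (A) was replaced by the following reduced form, with the growth rate constant eliminated".
- If the series rises continuously and only g has P<0.05, "Equation (A) was replaced by the following reduced form, with the decay constant eliminated".

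Section 8.1.4 attempts Equation (A) in each patient and adds: "We will extract parameters g and d with their associated Student's t and P values". It gives no other rule for choosing a model.

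The power statement in 8.1.1 begins "With growth rate changes obtained on all patients on both arms" and continues "with 17 patients per arm, there would be 80% power to detect a difference between the arms equal to 1 SD", "with a two-tailed 0.05 significance level two-group t-test". Patients without a 25% PSA decline at 3 months are not evaluated for re-growth. The accrual ceiling of 38 provides 38 - 34 = 4 extra patients, for that reason only.

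The plan is silent on four cases: the growth value of a patient whose g has been eliminated; whether he counts as evaluable; what happens when neither parameter is significant; and what happens when one is significant but the series is not monotone.

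**The concern.** The parameter being compared is also the one being tested for removal. A patient whose PSA stays low after enzalutamide stops, or climbs slowly, is the patient the vaccine is meant to produce. He is also the patient whose g is hardest to distinguish from zero. If he leaves the t-test, missingness depends on the outcome and, when the vaccine works, on the arm. Arm B then loses more of its slow re-growers than Arm A. The remaining patients look more alike, and the numbers fall below the 17 per arm on which the power rests. If he is kept at g = 0, the estimate moves the other way. A primary endpoint should not leave that choice to the analyst.

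**Working it through.** **1. The plan's own figure.** Inputs from 8.1.1: 17 per arm, difference 1 SD, two-sided 0.05, two-group t-test. Noncentrality = 1 × √(17·17/34) = √8.5 = 2.92 on 32 df. Exact noncentral-t power is 80.7%, so the stated 80% reproduces, provided all 34 patients have a growth rate.

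**2. Loss of numbers alone.** The same formula with patients missing:

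| Patients with g | Power at 1 SD |
|---|---|
| 17 v 16 | 79.4% |
| 17 v 15 | 78.0% |
| 17 v 13 | 74.5% |
| 15 v 15 | 75.3% |
| 14 v 14 | 72.1% |

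**3. Why a deep nadir removes g.** For small g, exp(g·t) - 1 is about g·t, so late in the series g must account for the PSA level as a fraction of baseline. With an assumed decay half-life of 8 days, f at day 14 is 2^(-14/8) = 0.30, and 10% noise on it is 0.03. In an unweighted fit that early noise sets the residual error. A nadir of 0.035 (96.5% decline) is comparable with it. A nadir of 0.003 (99.7% decline) is a tenth of it, so g is often not significant unless re-growth is quick.

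**4. How often only d is significant.** Simulated PSAs at the Appendix C visits (weeks 1, 3, 5, 9, 13, 15, 17, 21, 25, 29) were fitted with Equation (A) from day 0 by least squares and classified on P-values alone. Assumed, not in the documents: 10% measurement noise, a decay half-life of 6 to 12 days, and the nadirs of 99% and deeper. The 96.5% decline is the bicalutamide figure in 1.2.7. The ranges span separate sets of fits.

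| PSA decline | Share losing g |
|---|---|
| 96.5% | 0-2% |
| 99%, doubling time 3 months or more | 2-4% in one set, 4-13% in another |
| 99.7%, doubling time 2-3 months or more | about 30-50% (sets: 30-50%, 35-43%, 38-56%) |

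**5. Who is lost.** Trial-level simulation with a control doubling time of 45 days, between-patient CV 30%, median nadir 0.5% of baseline, half-life 12 days, and the vaccine slowing re-growth by 1 SD:

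- g is eliminated in 11.2% of control and 19.3% of vaccine patients.
- True re-growth per day, eliminated v kept on Equation (A): 0.0128 v 0.0159 (control) and 0.0089 v 0.0112 (vaccine).
- Patients left: 17 × 0.888 = 15.1 v 17 × 0.807 = 13.7. From step 2, power at 1 SD lies between 72.1% and 75.3% from the lost numbers alone.
- Difference in mean true rate: 0.0156 - 0.0108 = 0.0048 with everyone, 0.0159 - 0.0112 = 0.0047 after dropping, a shrinkage of about 2%.
- Mean fitted g in the vaccine arm: 0.00022 with everyone, 0.00025 if eliminated patients are dropped, 0.00020 if they are set to zero. The unstated choice moves the arm mean in opposite directions.
- Simulated power: 12.9% if dropped, 17.9% if set to zero. Both are low mainly because Equation (A) is fitted from day 0. With no reduction rule at all it is 18.4%.

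**6. With the monotonicity condition enforced.** At most 7% of simulated patients in any arm had a series that fell continuously to week 29. In the patient-level fits with this condition added, nobody lost g.

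**7. An ungated measure.** The log-PSA slope over weeks 13-29 in every evaluable patient gave 73-82% power across the same trial-level scenarios.

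**The case against.** The strongest reply is that the text is narrower than the concern. The g-eliminating form also requires a continuous decrease, which a patient whose PSA is rising, however slowly, does not meet; step 6 shows how little is then lost. Further, the reduced form is Equation (A) with g = 0, since exp(0) - 1 = 0, so recording zero is at least as natural as dropping the patient. The paragraph is in the past tense and cites earlier work. At the only decline the protocol quotes, the loss is 0-2%.

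Much of this stands, and it limits the size. It does not close the gap. The paragraph sits in Statistical Considerations and is the only model-choice rule there. Section 8.1.4 describes its planned t-test in the past tense too, so tense does not separate background from plan. Section 1.2.7 expects enzalutamide to do at least as well as a 96.5% decline, so deeper nadirs are within the protocol's own expectation. The zero reading is nowhere written down.

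Three stronger readings are tempting but not supported.

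- **Fast re-growers receive a negative g.** This needs the growth-only form applied on P-values alone. That form requires a continuous increase, and an evaluable patient must first show a 25% PSA fall. None of about 19,200 simulated patients qualified. Simulated power of 0.1-14% and wrong-direction results in up to 21% of trials came from P-value-only classification that allowed this form, so they are not consequences of the written rule.
- **Power falls from 0.79 to 0.34.** That figure comes from discarding non-significant log-PSA slopes over weeks 13-29 at a 6-month median doubling time. The plan states no such filter. Equation (A) fitted from week 13 gave only-d significance in 0% of simulated patients.
- **Re-growth after enzalutamide will be slow.** The remark in 1.2.9 that "growth rate resumed at the same pre-treatment rate once cytotoxic therapy was discontinued" concerns chemotherapy in metastatic castration-resistant disease. The documents give no re-growth speed for this setting.

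**Conclusion.** The concern holds as a gap in the primary analysis. Section 8.1.3 allows g to be removed by a significance test on the fitted constants and assigns no value afterwards, while 8.1.1 assumes a growth rate from every patient and holds reserve only for PSA non-decliners. If P-values decide and patients without g are dropped, the bias is toward no difference, because the losses fall on slow re-growers. Its size cannot be fixed from the documents. It is negligible at a 96.5% decline or if the continuous-decrease condition is enforced, modest at 99%, and substantial among slow re-growers at 99.7%. These sizes depend on the assumed noise, nadir and re-growth speed. The direction does not, but it does depend on dropping rather than zeroing. The cases where significance and monotonicity disagree are an ambiguity to resolve, not evidence of sign reversal. Starting the fit at treatment start rather than at discontinuation is a separate problem of at least equal weight; day-0 Equation (A) gave 17-38% power even without the reduction rule.

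**What to change.** For the primary endpoint, remove the P<0.05 reduction rule from 8.1.3 and from its copy in 1.2.10.1. State that every evaluable patient contributes one pre-specified growth measure over the primary window, for example the slope of log PSA from week 13 to week 29. It counts whatever its P-value, with zero and negative values allowed. State in advance how undetectable PSA values enter that measure. Keep Equation (A) and its reduced forms as a descriptive sensitivity analysis, saying there what value a patient without g receives and which condition governs when significance and monotonicity disagree.

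The cost is one paragraph. The PSAs at weeks 13, 15, 17, 21, 25 and 29 are already scheduled, and the window matches the month 3 to month 7 comparison in 8.1.1. The drawback is that some individual slopes will be imprecise. That imprecision enters the between-patient SD used by the t-test.

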8.1.4 Data Analysis

For each patient an attempt to fit Equation (A) to each data set for which more than one data point is available. Curve fitting will be performed using Sigmaplot (Systat Software), or by

Version Date: 12/5/17

Abbreviated Title: Enzalutamide in non-met CSPC

using the Solver routine in an Excel spreadsheet. We will extract parameters g and d with their associated Student's t and P values. (44) Data will be analyzed in Excel (Microsoft) and in Sigmaplot 9.0. Linear regressions to evaluate the relationship between the growth rate constant, g , or other parameters will be implemented using the polynomial linear routine of Sigmaplot 9.0. Sample comparisons were performed by Student's t -test, using SigmaStat 3.5 (Systat Software), with P set at 0.05 for significance. (44)

9 COLLABORATIVE AGREEMENTS

9.1 AGREEMENT TYPE

9.1.1 Cooperative Research and Development Agreement (CRADA)

- A CRADA (#02859) is in place with Medivation and Astellas to provide enzalutamide.
- A CRADA (#02377) is in place with Bavarian Nordic to provide PSA-TRICOM.

9.1.2 Material Transfer Agreement (MTA)

- A MTA is in place with The Cleveland Clinic Foundation for the studies discussed in section 4.1.6 (MTA#4122006).

10 HUMAN SUBJECT PROTECTIONS

10.1 RATIONALE FOR SUBJECT SELECTION

10.1.1 Selection Based on Gender, Ethnicity, and Race

Subjects from all racial/ethnic groups are eligible for this study if they meet the eligibility criteria. To date, there is no information that suggests that differences in drug metabolism or disease response would be expected in one group compared with another. Efforts will be made to extend accrual to a representative population, but in this preliminary study, a balance must be struck between patient safety considerations and limitations on the number of individuals exposed to potentially toxic and/or ineffective treatments on one hand and the need to explore ethnic aspects of clinical research on the other hand. If differences in outcome that correlate with ethnic identity are noted, accrual may be expanded or a follow-up study may be written to investigate those differences more fully. Women are not eligible for this study as this disease occurs only in men.

10.1.2 Strategies/Procedures for Recruitment

Patient accrual for this protocol will be facilitated by Web-based recruitment strategies. This protocol will be listed on www.clinicaltrials.gov.

10.1.3 Justification for Exclusions

Due to impaired cellular immunity with the concomitant increased risk of serious side effects from vaccinations with infectious agents, the Centers for Disease Control and Prevention recommends that HIV infected patients be excluded, in addition, patients with chronic hepatitis infection, including B and C, because of potential immune impairment.

10.2 PARTICIPATION OF CHILDREN

Men under the age of 18 will not be eligible for participation in this study based on the fact that patients under 18 are unlikely to have this disease and there are unknown toxicities in pediatric patients.

10.3 PARTICIPATION OF NIH SUBJECTS UNABLE TO GIVE CONSENT

Adults unable to give consent are excluded from enrolling in the protocol. However re-consent may be necessary and there is a possibility, though unlikely, that subjects could become decisionally impaired. For this reason and because there is a prospect of direct benefit from research participation (section 7.5), all subjects will be offered the opportunity to fill in their wishes for research and care, and assign a substitute decision maker on the “NIH Advance Directive for Health Care and Medical Research Participation” form so that another person can make decisions about their medical care in the event that they become incapacitated or cognitively impaired during the course of the study. Note: The PI or AI will contact the NIH Ability to Consent Assessment Team for evaluation. For those subjects that become incapacitated and do not have pre-determined substitute decision maker, the procedures described in MEC Policy 87-4 for appointing a surrogate decision maker for adult subjects who are (a) decisionally impaired, and (b) who do not have a legal guardian or durable power of attorney, will be followed.

10.4 EVALUATION OF BENEFITS/RISKS/DISCOMFORTS

There is no standard therapy for patients with prostate cancer and rising PSA following local definitive therapy. Potential risks of vaccine and enzalutamide therapy in this patient population include the range of side effects outlined in section 9. Both drugs have been well tolerated in previous large trials and there are no anticipated overlapping toxicities for patients getting both drugs.

10.4.1 Alternative Approaches or Treatments

Patients will be advised verbally and in writing regarding the risks and benefits of this trial, treatment requirements, and alternative approaches to entering the trial. Written consents will be obtained.

10.4.2 Procedures to Eliminate or Minimize Potential Risks

This study may involve unforeseeable risks for patients, such as side effects whose exact nature and severity are unpredictable. Scrupulous care will be taken to minimize such side effects. All patients will be given blood tests, physical examinations, and scans, as described in the monitoring schedule ([Appendix C](#)), and must have a local physician to provide long-term care and monitoring for complications. Immediate medical treatment is available at the Clinical Center, NCI, Bethesda, Maryland, for any patients who suffer physical injury as a result of participation in this study. No compensation is available, but any injury will be evaluated and treated in keeping with the benefits or care to which patients are entitled under applicable regulations.

10.4.3 Provisions for Monitoring Data Collection to Ensure Subject Safety

As information is gathered from this trial, clinical results will be shared with patients. Laboratory and clinical data will be frequently gathered and any new significant finding(s) found during the course of the research, which may affect a patient's willingness to participate further, will be explained.

Confidentiality of information concerning participants will be maintained, including in all publications and presentations resulting from this study. Names of participants or material identifying participants will not be released without permission, except as such release is required by law. Records at the National Cancer Institute are maintained according to current legal requirements, and are made available for review, as required by the Food and Drug Administration or other authorized users, only under the guidelines established by the Federal Privacy Act.

10.5 RISKS/BENEFITS ANALYSIS

This study involves clinical research with an experimental vaccine designed to generate an immune response against antigens found in prostate cancer. Patients will undergo multiple vaccinations. Side effects of the vaccine are outlined elsewhere (see section 11). Whether the vaccine will have any clinical effect is unknown; therefore, benefit cannot be promised, nor the chance of benefit accurately predicted. Enzalutamide is an FDA-approved therapy with a known and minimal toxicity profile (section 11). Participation in this study is voluntary, and refusal will not result in penalty or loss of benefit to which the patient is otherwise entitled.

The standard of care for patients with nmCSPC includes ADT and active surveillance. Generally, these patients can be followed without therapy until their PSA doubling time escalates at which time ADT is often started. All patients in the proposed trial will receive enzalutamide. Based on previous trials with high dose bicalutamide, 34 of 36 evaluable patients had PSA declines by a median of 96.5% and these nadirs were achieved within the first 4 weeks of treatment (10). We would expect similar if not better results with enzalutamide. Therefore, a clinical trial in this population is ethical and appropriate. The NCI has conducted several trials in this population previously.

Participation may be discontinued at any time without penalty, and the patient will be encouraged to discuss any concerns or questions.

